**Table 6-6 Dose Reduction steps for nazartinib**

Dose level	Proposed daily dose of nazartinib
0	nazartinib 100 mg q.d.
-1	nazartinib 75 mg q.d.
-2	nazartinib 50 mg q.d.

Note: dose reduction should be based on the worst toxicity demonstrated at the last dose

**Table 6-7 Criteria for dose reduction, interruption and re-initiation of nazartinib and capmatinib for adverse drug reaction**

Worst toxicity CTCAEa Grade (value)	Recommendation
HEMATOLOGICAL	
Neutrophil count decreased (ANC) Neutropenia	
Grade 1 (ANC < LLN - 1500/mm  ; < LLN - 1.5 x 10  /L)	Maintain dose levels of nazartinib and capmatinib
Grade 2 (ANC < 1500 - 1000/mm  ; < 1.5 - 1.0 x 10  /L)	Maintain dose levels of nazartinib and capmatinib
Grade 3 (ANC <1000 – 500/mm  )	
Omit study treatment until resolved to ≤ grade 2, then resume nazartinib at the same dose level:
 
 
• If fully resolved in ≤ 7 days, then resume capmatinib at same dose level
 
• If fully resolved in > 7 days, then resume capmatinib at ↓ 1 dose level
 
• If recurrence of grade 3 toxicity on maintained dose of nazartinib and ↓ 1 dose level of capmatinib, omit study treatment until resolved to ≤ grade 2, then resume nazartinib at ↓ 1 dose level and the same dose level of capmatinib (i.e., both study drugs ↓ 1 dose level from dose levels at initial occurrence of grade 3 AE)
 
• If recurrence of grade 3 during nazartinib monotherapy, omit study treatment until resolved to ≤ grade 2, then resume nazartinib at ↓ 1 dose level
 
• If no recurrence of grade 3 toxicity after 7 days of nazartinib monotherapy at ↓ 1 dose level, resume capmatinib at same dose level
 

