Grade $\geq$ 3 (despite standard anti-emetics)	
Omit study treatment until resolved to <math>\leq</math> grade 1, then resume nazartinib at same dose level
 
 
• If no recurrence of grade 3 toxicity after 7 days of nazartinib monotherapy, resume capmatinib at <math>\downarrow</math> 1 dose level
 
• If recurrence of grade 3 toxicity during nazartinib monotherapy, omit study treatment until resolved to <math>\leq</math> grade 1, then <math>\downarrow</math> 1 dose level capmatinib
 
• If no recurrence of grade 3 toxicity after 7 days of capmatinib monotherapy at <math>\downarrow</math> 1 dose level, resume nazartinib at same dose level
 

Vomiting	
Grade 1	Maintain dose levels of both study drugs but adjust anti-emetic treatment
Grade 2 (despite standard anti-emetics)	Omit study treatment until resolved to $\leq$ grade 1, then maintain dose levels of both drugs.
Grade $\geq$ 3 (despite standard anti-emetics)	Omit study treatment until resolved to $\leq$ grade 1, then resume nazartinib at same dose level

Worst toxicity CTCAEa Grade (value)	Recommendation
	
 
If no recurrence of grade 3 toxicity after 7 days of nazartinib monotherapy, resume capmatinib at ↓ 1 dose level
 
If recurrence of grade 3 toxicity during nazartinib monotherapy, omit study treatment until resolved to ≤ grade 1, then ↓ 1 dose level capmatinib
 
If no recurrence of grade 3 toxicity after 7 days of capmatinib monotherapy at ↓ 1 dose level, resume nazartinib at same dose level
 

Grade 4 (despite standard anti-emetics)	Discontinue study treatment
Dose modifications apply to participants who experience nausea and/or vomiting despite appropriate antiemetic medication. This medication should be started at the first sign of nausea and/or vomiting.	
SKIN AND SUBCUTANEOUS TISSUE DISORDERS	
Stevens-Johnson Syndrome (SJS) or Lyell syndrome/Toxic Epidermal Necrolysis (TEN)	Permanently discontinue study treatment and manage per institutional guidelines.
Rashl	
Grade 1 Macules/papules covering <10% BSA (Body Surface Area)	Maintain dose levels of nazartinib and capmatinib
Grade 2 Macules/papules covering 10 - 30% BSA	Maintain dose levels of nazartinib and capmatinib

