Grade ≥3	Omit study treatment until resolved to ≤ grade 1, then resume nazartinib at same dose level of and re-evaluate after 7 days, or sooner if clinically indicated 
 
• If no recurrence of grade 3 toxicity after 7 days of nazartinib monotherapy, resume capmatinib at ↓ 1 dose level
 
• If recurrence of grade 3 toxicity on maintained dose level of nazartinib and ↓ 1 dose level of capmatinib, omit study treatment until resolved to ≤ grade 1, then resume nazartinib at ↓ 1 dose level and maintain dose level of capmatinib (i.e., both study drugs ↓ 1 dose level from levels at initial occurrence of grade 3 AE)
 
• If recurrence of grade 3 toxicity during nazartinib monotherapy, omit study treatment until resolved to ≤ grade 1, then nazartinib at ↓ 1 dose level
 
• If no recurrence of grade 3 toxicity after 7 days of nazartinib monotherapy at ↓ 1 dose level, resume capmatinib at ↓ 1 dose level
 

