g Note: If total bilirubin > 3.0 × ULN is due to the indirect (non-conjugated) component only, and hemolysis as the etiology has been ruled out as per institutional guidelines (e.g., review of peripheral blood smear and haptoglobin determination), then ↓ 1 dose level and continue treatment at the discretion of the investigator. h A CT scan or other imaging study to assess the pancreas, liver, and gallbladder must be performed within 1 week of the first occurrence of any ≥ grade 3 of amylase and/or lipase. If asymptomatic grade 2 elevations of lipase and/or amylase occur again at the reduced dose, participants will be discontinued permanently from study treatment. i Antidiarrheal medication is recommended at the first sign of abdominal cramping, loose stools or overt diarrhea. j During the whole duration of treatment with capmatinib, the participant is recommended to use precautionary measures against ultraviolet exposure (e.g., use of sunscreen, protective clothing and avoid sunbathing or using a solarium intensively).	

**Table 6-8 Dose modifications for capmatinib monotherapy (or if nazartinib permanently discontinued and capmatinib continued as monotherapy)**

Worst toxicity CTCAE Grade a during a cycle of therapy	Recommendation
No toxicity	Maintain dose level
HEMATOLOGICAL	
Neutrophil count decreased (ANC) Neutropenia	
Grade 1 (ANC < LLN - 1500/mm  ; < LLN - 1.5 x 10  /L)	Maintain dose level
Grade 2 (ANC < 1500 - 1000/mm  ; < 1.5 - 1.0 x 10  /L)	Maintain dose level
Grade 3 (ANC < 1000 - 500/mm  ; < 1.0 - 0.5 x 10  /L)	Omit dose until resolved to ≤ grade 2, then: 
 
• If fully resolved in ≤ 7 days, resume treatment at the same dose level
 
• If fully resolved in > 7 days, then resume at ↓ 1 dose level
 

Grade 4 (ANC < 500/mm  ; < 0.5 x 10  /L)	Omit dose until resolved to ≤ grade 2 and then resume at ↓ 1 dose level
Platelet count decreased (Thrombocytopenia)	
Grade 1 (PLT < LLN - 75,000/mm  ; < LLN - 75 x 10  /L)	Maintain dose level
Grade 2 (PLT < 75,000 - 50,000/mm  ; < 75 - 50 x 10  /L)	Maintain dose level

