Grade 1 or 2	Maintain dose level, consider to initiate appropriate support medication. For any intolerable grade 2 (e.g. limiting instrumental activities of daily living), consider omitting the dose until resolved to ≤ grade 1, then resume either at same dose or ↓ 1 dose level.
Grade 3	Omit dose until resolved to ≤ grade 1, then resume at ↓ 1 dose level
Grade 4	Permanently discontinue capmatinib

All dose modifications should be based on the worst preceding toxicity.
 
a Common Toxicity Criteria for Adverse Events (CTCAE version 5.0).
 
b “Combined” defined as: total bilirubin increase to the defined threshold concurrently with ALT/AST increase to the defined threshold
 
c “Cholestasis” defined as: ALP elevation (> 2.0 x ULN and R value (ALT/ALP in x ULN) < 2.0) in participants without bone metastasis, or elevation of ALP liver fraction in participants with bone metastasis
 
d If combined elevations of AST or ALT and total bilirubin do not meet the defined thresholds, please follow the instructions for isolated elevation of total bilirubin and isolated elevation of AST/ALT, and take a conservative action based on the degree of the elevations (e.g. discontinue treatment at the situation when omit dose is needed for one parameter and discontinue treatment is required for another parameter). After all elevations resolve to the defined thresholds that allow treatment re-initiation, re-start the treatment either at the same dose or at one dose lower if meeting a criterion for dose reduction
 
* Note: If total bilirubin > 3.0 x ULN is due to the indirect (non-conjugated) component only, and hemolysis as the etiology has been ruled out as per institutional guidelines (e.g., review of peripheral blood smear and haptoglobin determination), then ↓ 1 dose level and continue treatment at the discretion of the investigator
 
** Note: antidiarrheal medication is recommended at the first sign of abdominal cramping, loose stools or overt diarrhea
 
*** During the whole duration of treatment with capmatinib, the participant is recommended to use precautionary measures against ultraviolet exposure (e.g., use of sunscreen, protective clothing and avoid sunbathing or using a solarium intensively)
	

**Table 6-9 Dose modifications for nazartinib (if capmatinib permanently discontinued and nazartinib continued as monotherapy)**

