Grade 4	Recommendation: omit dose and then discontinue nazartinib. Note: Omit dose for $\geq$ grade 3 vomiting or grade 3 nausea only if the vomiting or nausea cannot be controlled with optimal antiemetic (as per local practice)
All dose modifications should be based on the worst preceding toxicity. a Common Terminology Criteria for Adverse Events (CTCAE) version 5.0 b If Grade 3 or 4 hyper-bilirubinemia is due to the indirect (non-conjugated) component only, and hemolysis as the etiology has been ruled out as per institutional guidelines (e.g., Review of peripheral blood smear and haptoglobin determination), then $\downarrow$ 1 dose level and continue treatment at the discretion of the investigator. c LFTs include albumin, ALT, AST, total bilirubin (fractionated if total bilirubin $>$ 2.0 x ULN), alkaline phosphatase (fractionated if alkaline phosphatase $>$ 2.0 x ULN) and gamma-glutamyl transpeptidase (GGT). For isolated elevations of any grade of alkaline phosphatase and/or GGT, maintain dose level. d "Combined" defined as: total bilirubin increases to the defined threshold concurrently with ALT/AST increase to the defined threshold	

Worst toxicity CTCAEa Grade (value) during a cycle of therapy	Recommendations

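### For a Grade 4 event in the Other adverse events category, the combination table (6-7) restarts treatment while the single-agent tables (6-8, 6-9) stop the drug, with no reason given; Table 6-7 also gives Grade 4 vomiting two actions

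*Protocol*

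**What the plan says.** Section 6.3.1 of the protocol gives three dose-modification tables, each for a different regimen.

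- Table 6-7 covers both drugs given together: "Criteria for dose reduction, interruption and re-initiation of nazartinib and capmatinib for adverse drug reaction".
- Table 6-8 covers capmatinib alone: "Dose modifications for capmatinib monotherapy (or if nazartinib permanently discontinued and capmatinib continued as monotherapy".
- Table 6-9 covers nazartinib alone: "Dose modifications for nazartinib (if capmatinib permanently discontinued and nazartinib continued as monotherapy".

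Each ends with a block for adverse events that have no row of their own. In Table 6-7 that block has two rows, Grade 1 or 2 and Grade ≥3. The second says "Omit study treatment until resolved to ≤ grade 1, then resume nazartinib at same dose level of and re-evaluate after 7 days", and for capmatinib "If no recurrence of grade 3 toxicity after 7 days of nazartinib monotherapy, resume capmatinib at ↓ 1 dose level". Tables 6-8 and 6-9 instead separate Grade 3 from Grade 4. Their Grade 4 rows say "Permanently discontinue capmatinib" and "Recommendation: omit dose and then discontinue nazartinib" respectively.

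In the vomiting block of Table 6-7, a Grade ≥3 row holds both drugs and then reintroduces them in sequence. It is followed by a row beginning "Grade 4 (despite standard anti-emetics", whose action is to end study treatment.

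**The concern.** A first Grade 4 event of the residual kind leads to different actions depending on the table in force. On either drug alone the entry is discontinuation. On the two together, both may come back, nazartinib at an unchanged dose. The protocol does not say why, and the wording leaves it unclear whether the Table 6-7 row was meant to cover Grade 4.

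The regimen where this operates now is Group 5. The Amendment 07 rationale states that no Phase Ib or Group 1 to 4 participant is still on treatment. Group 5 participants start on capmatinib under Table 6-8 and may add nazartinib at radiological progression, which brings them under Table 6-7. Table 3-1 makes safety and tolerability (interruptions, reductions, dose intensity) secondary endpoints for Group 5 on monotherapy and on the combination. If the handling of the same kind of event differs between the two periods because of drafting, part of any difference in those tolerability measures reflects the rule rather than the drugs. For vomiting, a site faces two instructions in one table.

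**Working it through.** No sample size, power or error rate is involved, so the check sets the rows side by side and looks for a rule that overrides them.

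**Step 1. First Grade 4 event in the Other adverse events category**

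| Table | Regimen | Row that applies | Action |
|---|---|---|---|
| 6-7 | Both drugs | Grade ≥3 (no separate Grade 4 row) | Hold both until Grade 1 or less; nazartinib restarts unchanged; capmatinib restarts one level lower if no Grade 3 recurrence in 7 days on nazartinib alone |
| 6-8 | Capmatinib alone | Grade 4 | Permanent discontinuation |
| 6-9 | Nazartinib alone | Grade 4 | Discontinuation, worded as a recommendation |

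**Step 2. Does the general text of Section 6.3.1 override the Table 6-7 row?** It requires discontinuation in two situations: a toxicity-related interruption of more than 21 days, and recurrence at the same or worse severity after restarting at a lower dose. Neither reaches a first Grade 4 event that resolves in time. The Table 6-7 footnotes contain no such rule either. The allowance for case-by-case exceptions permits departures but does not tell a site what the default is.

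**Step 3. Was the row written with Grade 4 in mind?** Its bullets speak only of Grade 3 toxicity and of the first Grade 3 event. Where Table 6-7 does plan a restart after Grade 4, in the neutropenia and thrombocytopenia rows, it refers to toxicity of Grade 3 or higher and to the first Grade 4 event. The label includes Grade 4; the text beneath it does not mention it. That is a reason to ask, not proof of an error.

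**Step 4. Vomiting in Table 6-7.** Grade 4 satisfies both Grade ≥3 and Grade 4. The first row restarts treatment in sequence, the second ends it. The two cannot both be followed.

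**Step 5. How far does the difference extend?** The residual category is not the same set of events in each table, and the direction of difference varies.

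- Bradycardia, hypophosphatemia and hyperglycemia have their own rows in Table 6-9 only. On the combination they fall to the residual row of Table 6-7. For hypophosphatemia of any grade Table 6-9 keeps the dose, so at Grade 3 or above Table 6-7 is the stricter. For Grade 4 bradycardia Table 6-9 either stops nazartinib or, where a contributing co-medication can be changed, restarts it one level lower. For persistent hyperglycemia it restarts one level lower once controlled, and stops if control fails.
- Grade 4 vomiting ends treatment under the specific row of Table 6-7, while Tables 6-8 and 6-9 restart one level lower.
- Grade 4 AST or ALT elevation stops both drugs in Table 6-7, while Table 6-9 allows nazartinib to restart in participants judged to benefit.

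The discrepancy in Step 1 is therefore confined to Grade 4 events that sit in the Other adverse events category of the single-agent table as well as of Table 6-7.

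**The case against.** The three tables govern different regimens, and no participant is under two of them at once. Different rules for different regimens are not in themselves a contradiction. With two drugs, holding both and reintroducing them in sequence may serve to identify the cause, and Table 6-7 uses that scheme widely. A Group 5 participant who stops capmatinib permanently under Table 6-8 would not ordinarily reach Table 6-7, so the before-and-after comparison is mostly between different participants. The restart is also conditional: resolution first, then 7 days on nazartinib alone, with the limits of Section 6.3.1 on top. The Table 6-9 entry is a recommendation. The combination is now an optional extension in a group of about 30.

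All of this stands, and it limits the size of the point. It does not supply the missing reason. Sequential reintroduction explains the scheme for Grade 3 but does not by itself settle Grade 4, because Table 6-7 permanently stops one or both drugs for many named Grade 4 toxicities, such as creatinine, bilirubin, AST or ALT, QTc prolongation and rash. The vomiting overlap lies inside one table and one regimen, so the argument about different regimens does not reach it. One may say that the specific Grade 4 row prevails, which is a sensible reading, but the table does not say so.

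A reader might infer that the combination rules are laxer than both single-agent rules throughout, or that every Grade 4 event without its own row meets opposite actions. Step 5 of the working shows that neither holds. A reader might also take the vomiting overlap as proof that the Grade ≥3 label is used carelessly everywhere. The diarrhea rows speak against that: Grade ≥3 restarts treatment in Table 6-7, and Grade 4 diarrhea also restarts in Tables 6-8 and 6-9.

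**Conclusion.** The point holds in a limited form. By its label, the residual Grade ≥3 row of Table 6-7 lets both drugs be restarted after a Grade 4 event, conditionally for capmatinib, whereas Tables 6-8 and 6-9 discontinue the drug for Grade 4 events in their own residual category. The protocol gives no reason. Grade 4 vomiting in Table 6-7 has two incompatible entries.

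No figure can be put on the effect: the protocol text reviewed states no rate for such events. It can arise only in Group 5 participants (about 30 planned) who take up the combination after progression. It bears on their safety management and on the secondary safety and tolerability endpoints. The primary endpoint, response rate on capmatinib monotherapy, is not affected, because Table 6-7 does not apply in that period. The conclusion rests on reading the row label literally and on finding no overriding rule in Section 6.3.1 or the footnotes. No view is taken on which action is right. The rows should be corrected or explained; nothing here calls the design into question.

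**What to change.** Reconcile the Grade 4 entries of the Other adverse events blocks in Tables 6-7, 6-8 and 6-9, or state that the difference is intended and why. Make the label and the bullets of the Table 6-7 row agree on whether Grade 4 is covered. Make the vomiting rows of Table 6-7 mutually exclusive, so that Grade 4 has one action. Which action applies in each case is for the clinical team to decide.

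The cost is table wording in the next amendment. Sample size, endpoints and the planned analyses do not change.
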